5.4 DRUG CONCENTRATION MEASUREMENTS AND PHARMACOKINETICS

5.4.1 Assessment of Pharmacokinetics

Date and clock time of drug administration and PK sampling will be recorded in the eCRFs.

The actual sampling times will be used for determination of PK parameters.

The PK endpoints to be evaluated are outlined in [Section 5.1](#).

5.4.2 Methods of sample collection

Plasma sampling for pharmacokinetic analysis

Samples of whole blood (approximately 3 mL) will be taken (in tubes containing dipotassium ethylenediaminetetraacetic acid [K₂EDTA] anticoagulant) at the time points shown in the [Flow chart](#) for the determination of concentrations of BI 695501.

Method to process the sample after collection will be described in the laboratory manual.

After completion of the trial, selected PK samples may be retained and used for further methodological investigations, e.g., stability testing. The PK samples will be discarded after completion of the additional investigations, but not later than 5 years after the final Clinical Trial Report (CTR) has been signed.

Wherever possible, blood samples for other analyses will be taken at the same time as blood is drawn for PK analyses to limit repeated venipuncture.

In the event of early withdrawal from the trial, every effort should be made to take a PK sample as part of the early withdrawal procedures, if possible, with date and time of sample recorded.

Boehringer Ingelheim
BI Trial No.: 1297.13
c11534380-01

Trial Protocol

23 Aug 2016

Page 40 of 58

Proprietary confidential information © 2016 Boehringer Ingelheim International GmbH or one or more of its affiliated companies

5.4.3 Analytical determinations

Plasma concentrations of BI 695501 will be measured using a validated method.

After completion of the trial, selected PK samples may be retained and may be analyzed for the presence of species (e.g., soluble proteins or small molecule entities) potentially interfering with the analysis method or for generation of ADA positive control material and stability testing for use in future assays. Retained samples may also be used to further characterize the immune response (e.g., isotyping of ADA) if required and as additional assay methods are developed. The results of any additional ADA analyses of the retained samples (i.e., analyses not already specified in this protocol) will be reported separately from the CTR.

All remaining trial samples will be discarded after completion of the additional investigations upon written authorization by the sponsor, but not later than 5 years after the final CTR has been signed.

5.4.4 Pharmacokinetic – Pharmacodynamic Relationship

Not applicable.

5.5 ASSESSMENT OF BIOMARKER(S)

Not applicable.

5.6 OTHER ASSESSMENTS

5.6.1 Assessment of immunogenicity

5.6.1.1 Plasma sampling for Anti-Drug-antibodies characterization

For characterization of human anti-BI 695501 antibodies (ADA), approximately 3 mL of blood will be collected from a forearm vein in a K₂EDTA anticoagulant blood drawing tube at time points indicated in [Flow Chart](#).

Method to process the sample after collection will be described in the laboratory manual. Anti-drug antibody will be detected in human plasma samples using validated methods. After completion of the trial, selected immunogenicity samples (ADA and nAb) may be retained and may be analyzed for the presence of species (e.g., soluble proteins or small molecule entities) potentially interfering with the analysis method or for generation of ADA positive control material and stability testing for use in future assays. Retained samples may also be used to further characterize the immune response (e.g., isotyping of ADA) if required and as additional assay methods are developed. The results of any additional ADA analyses of the retained samples (i.e., analyses not already specified in this protocol) will be reported separately from the CTR.

Boehringer Ingelheim
BI Trial No.: 1297.13
c11534380-01

23 Aug 2016

Trial Protocol

Page 41 of 58

Proprietary confidential information © 2016 Boehringer Ingelheim International GmbH or one or more of its affiliated companies

All remaining trial samples will be discarded after completion of the additional investigations upon written authorization by the sponsor, but not later than 5 years after the final CTR has been signed.

5.6.1.2 Plasma sampling for neutralizing antibody characterization

For characterization of human neutralizing anti-BI 695501 antibodies (nAb), approximately 6 mL of blood will be collected from a forearm vein in a K₂EDTA anticoagulant blood drawing tube at the same time points as ADA samples are collected. Method to process the sample after collection will be described in the laboratory manual.

Neutralizing antibodies will be detected in human plasma samples using validated methods.

5.7 APPROPRIATENESS OF MEASUREMENTS

All measurements performed during this trial are standard measurements and will be performed in order to monitor subjects' safety and to determine PK parameters in an appropriate way. The scheduled measurements will allow monitoring of changes in vital signs, standard laboratory values, and ECG parameters that might occur as a result of administration of trial medication. The safety assessments are standard, are accepted for evaluation of safety and tolerability of a subcutaneously administered drug, and are widely used in clinical trials. The PK parameters and measurements outlined in [Section 5.1](#) are generally used assessments of drug exposure. Therefore, the appropriateness of all measurements applied in this trial is confirmed.

Boehringer Ingelheim
BI Trial No.: 1297.13
c11534380-01

Trial Protocol

23 Aug 2016

Page 42 of 58

Proprietary confidential information © 2016 Boehringer Ingelheim International GmbH or one or more of its affiliated companies

6. INVESTIGATIONAL PLAN

6.1 VISIT SCHEDULE

Exact times of measurements outside the permitted time windows will be documented. The acceptable time windows for all visits are given in [Flow Chart](#).

- General medical examination: at screening (2 to 28 days prior to the first trial day);
- Trial measurements and assessments scheduled to occur 'before' trial medication administration on Day 1 are to be performed and completed within a 2 hour period prior to the trial drug administration.
- The acceptable deviation from the scheduled time for vital signs, ECG and laboratory tests PK, ADA, nAb sampling) will be:
 - ± 15 minutes for Day 1
 - ± 2 hours from Day 2 to Day 10;
 - ± 1 day from Day 15 to Day 57
 - The e.o.t. IGRA may be performed up to 72 hours prior to the other e.o.t. assessments.

If scheduled in the Flow Chart at the same time as a meal, vital signs, 12-lead ECG recordings and blood sampling have to be done first. Furthermore, if several measurements including venipuncture are scheduled for the same time, venipuncture should be the last of the measurements due to its inconvenience to the subject and possible influence on physiological parameters.

For planned individual plasma concentration sampling times refer to Flow Chart. While these nominal times should be adhered to as closely as possible, the actual sampling times will be recorded and used for determination of PK parameters.

If a subject misses an appointment, it will be rescheduled if possible. The relevance of measurements outside the permitted time windows will be assessed no later than at the Report Planning Meeting.

6.2 DETAILS OF TRIAL PROCEDURES AT SELECTED VISITS

6.2.1 Screening Period

After having been informed about the trial, all subjects will give their written informed consent in accordance with GCP and local legislation prior to enrolment in the trial. For information regarding laboratory tests (including drug and virus screening), ECG, vital signs, and physical examination, refer to [Sections 5.3.1 to 5.3.5](#). If possible, spare subjects will be provided for each group to guarantee the start of a complete group. The spare subjects will participate in all trial activities up to Day 1, i.e. on Day -1 they will be admitted to the clinic and all examinations, which have been scheduled up to drug administration on Day 1 will be performed. The spare subjects from one group will be given the option to participate in the next planned group.

Boehringer Ingelheim
BI Trial No.: 1297.13
c11534380-01

23 Aug 2016

Trial Protocol

Page 43 of 58

Proprietary confidential information © 2016 Boehringer Ingelheim International GmbH or one or more of its affiliated companies

6.2.2 Treatment period(s)

Subjects will be randomly allocated to the treatment (autoinjector or prefilled syringe).

On Day -1 trial participants will be admitted to the trial site and kept for 8 days following drug administration. The subjects will be allowed to leave the trial site from Day 8 after formal assessment and confirmation of their fitness. On all other trial days, the trial assessments will be performed in an ambulatory fashion.

For details on time points and procedures for collection of plasma samples for PK, ADA and nAb analysis, refer to [Flow Chart](#) and [Section 5.5](#).

The safety measurements performed during the treatment period are specified in [Section 5.3](#) of this CTP and in Flow Chart. For details on time points for all other trial procedures, refer to Flow Chart. Adverse events and concomitant therapy will be assessed continuously from screening until the end of trial.

6.2.3 Follow Up Period and Trial Completion

For AE assessment, laboratory tests, recording of ECG and vital signs, and physical examination during the end of treatment (e.o.t.) visit (day 57), see [Sections 5.3.1 to 5.3.5](#).

Subjects who discontinue trial participation before the end of the planned observational period but not withdraw consent - should undergo the e.o.t. visit and Safety Follow-up (end of trial) visit 10 weeks after administration of the trial medication.

All abnormal values (including laboratory parameters) that are judged clinically relevant by the investigator will be monitored using the appropriate tests until a return to a medically acceptable level is achieved. Adverse events persisting after trial completion must be monitored until they have normalized or have been sufficiently characterized.

The end of the trial as a whole is defined by the ‘last regular visit completed by last subject’ or ‘end date of the last open AE’ or ‘date of the last follow-up test’ or ‘date of an AE has been decided as sufficiently followed-up’, whichever is latest.

Long-term safety follow-up observational period will continue for 10 weeks after BI 695501 administration to collect AEs (SAEs).

The subjects are to be instructed to contact the investigator or his/her designee in case of occurrence of any AEs, any additional concomitant drug or if they undergo any medical treatment or any surgical procedure during the observational period until the safety follow-up visit call. Subjects will be contacted by the investigator or designee 10 weeks after administration of the trial medication to collect the information on subject’s wellbeing and document all AEs (SAEs) and concomitant medication.

All AEs, serious and non-serious, will be followed up until they have normalized or been sufficiently characterized and documented in the safety database.

7. STATISTICAL METHODS AND DETERMINATION OF SAMPLE SIZE

This is a randomized, open-label, parallel-group, single-dose, Phase I trial.

7.1 STATISTICAL DESIGN - MODEL

For the purposes of the exploratory analysis, the primary PK endpoints for BI 695501 will be estimated using an analysis of variance (ANOVA) model on the logarithmic scale with fixed effects for treatment, and baseline body weight (continuous).

The ANOVA model is described by the following equation:

$$y_{ij} = \mu + \tau_i + \beta * \text{weight}_{ij} + e_{ij}, \text{ where}$$

y_{ij} = logarithm of PK parameter measured on subject j receiving treatment i,

μ = the overall mean,

τ_i = the i-th treatment effect, $i = 1, 2$ (1=Test, 2=Reference),

β = the slope parameter for the baseline body weight covariate,

weight_{ij} = baseline body weight of subject j receiving treatment i,

e_{ij} = the random error associated with the j-th subject, receiving treatment i,

where $e_{ij} \sim N(0, \sigma_i^2)$ are independent random variables.

The randomisation will be stratified by site, but this is considered to be a logistical stratification and will therefore be not included in the primary model.

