Title of trial:	Randomized, single-dose, parallel-arm, open-label Phase I trial to compare the pharmacokinetics, safety and tolerability of BI 695501 administered subcutaneously via prefilled syringe or autoinjector		
Coordinating Investigator:	[REDACTED]		
Trial sites:	Multicenter trial to be conducted in three two countries: SGS Life Science Services – Clinical Research Clinical Pharmacology Unit Antwerpen [name] PRA HealthSciences [name]		
Clinical phase:	I		
Objective(s):	The primary objective of this trial is to characterize and compare the pharmacokinetics of BI 695501 after subcutaneous injection using either a prefilled syringe or an autoinjector. Additionally, safety, tolerability and immunogenicity will be assessed.		
Methodology:	This is a randomized, single-dose, open-label trial in healthy volunteers in two sites. This trial will consist of two parallel arms receiving BI 695501 by either a prefilled syringe or an autoinjector.		
No. of patients:	160 healthy male and female subjects with evaluable PK data for primary analysis. At least 30% of each gender will be included in the study.		
total entered:	Consisting of: 
 • subjects with a baseline body weight ≤ 60.0 kg, • subjects with a body weight >60.0 - <90.0 kg, • subjects with a body weight ≥90.0 kg 		
each treatment:	BI 695501/ prefilled syringe – up to 80 subjects BI 695501/ autoinjector – up to 80 subjects		
Diagnosis :	Not applicable		

Boehringer Ingelheim
BI Trial No.: 1297.13
c11534380-01

Trial Protocol

23 Aug 2016

Page 3 of 58

Proprietary confidential information © 2016 Boehringer Ingelheim International GmbH or one or more of its affiliated companies

Name of company:		Boehringer Ingelheim	
Name of finished product:		NA	
Name of active ingredient:		BI 695501	
Protocol date: 23 Aug 2016	Trial number: 1297.13		Revision date:
Main criteria for inclusion:	Healthy male and female subjects aged ≥ 18 to ≤ 65 years and body mass index range: >17.5 to < 35.0		
Test product(s): dose: mode of administration:	BI 695501 solution for injection/autoinjector 40 mg (0.8 mL) Subcutaneous injection via autoinjector		
Comparator products: dose: mode of administration:	BI 695501 solution for injection/pre-filled syringe 40 mg (0.8 mL) Subcutaneous injection via prefilled syringe		

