- The potential for BI 695501 to induce *in vitro* cytokine release or directly activate complement compared to EU-approved Humira. The results from this trial demonstrated that BI 695501 and EU-approved Humira are not anticipated to induce cytokine release in humans and do not directly activate complement.
- An irritation potential trial in rabbits with BI 695501 demonstrated that BI 695501 did not cause irritation.

To date, a total of 175 male healthy subjects were treated with 40 mg s.c. of BI 695501 administered via prefilled glass syringe in two healthy subject trials 1297.1 and 1297.8 ([U13-1096-01](#) and [c03070713](#)). The PK similarity of BI 695501 to US-licensed Humira and EU-approved Humira was demonstrated in a healthy volunteers study using the final commercial formulation ([c03070713](#)) in study 1297.8. Single s.c. doses of 40 mg BI 695501, US-licensed Humira and EU-approved Humira were generally well tolerated by healthy male subjects. There were no notable differences between the 3 treatment arms with respect to safety, tolerability and immunogenicity.

Additionally, 71 healthy volunteers were treated in a Phase I trial (1297.6, [c02715841](#)), comparing the PK of BI 695501 administered using an autoinjector or a prefilled syringe following s.c. injection in the abdominal area. Preliminary results of 66 completed subjects showed no clinically relevant differences in PK, safety and immunogenicity. Overall, the adverse events (AEs) seen in three healthy subject trials for BI 695501 and both EU-approved Humira and US-licensed Humira were in line with the known safety profile presented in the US prescribing information for US-licensed Humira ([R16-2901](#)) and in the summary of product characteristics (SPC) for EU-approved Humira ([R16-2926](#)).

A phase III trial (1297.2) in patients with moderate to severe RA is ongoing and recruitment has been completed; 645 patients with moderate to severe RA were included and randomized to treatment with BI 695501 or US-licensed Humira in a blinded manner. The observed blinded AE profile revealed no unexpected safety findings and showed no clinically relevant safety concerns. The extension trial to the RA trial (1297.3) is ongoing where patients with benefit on the pivotal trial are treated with Bi 695501 in an open label fashion.

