3.2 DISCUSSION OF TRIAL DESIGN, INCLUDING THE CHOICE OF CONTROL GROUP(S)

This is a 14-week, open-label, randomized, single dose, parallel arm trial to investigate and compare the PK, safety, tolerability and immunogenicity of BI 695501 administered subcutaneously in the thigh via prefilled syringe or autoinjector.

Due to the long half-life of BI 695501, a parallel group design was selected, with administration of BI 695501 as a single dose only. Additionally, randomization minimizes selection bias between the treatment groups.

Blinding is not possible because the BI 695501 presentations are visually distinguishable. The open-label treatment is not expected to bias the PK results, since the trial endpoints are derived from measurement of plasma concentrations of the analyte provided by a bioanalytical laboratory which is blinded to treatment allocation.

It is not expected that the device itself, being a prefilled syringe or an autoinjector, has an influence on the bioavailability in terms of rate and extent of absorption especially considering the long half-life of the compound. The most likely important variable is the reliability of the injection with regards the depth of the injection and thus the tissue reached as well as the amount of drug being injected by the device. The injection characteristics are

more likely influenced by the amount of s.c. fat tissue. Body mass index and weight have a good correlation with s.c. fat tissue thus the inclusion of healthy subjects having a broad range of weight would give a better estimation of the reliability and performance of the devices.

The group size of up to 80 subjects per treatment group is considered adequate for an evaluation of the PK, safety, tolerability, and immunogenicity for the primary analysis report to support the primary objective of the study.

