7.7 DETERMINATION OF SAMPLE SIZE

It is planned to enter a total of 160 subjects for the primary analysis of this trial, because this sample size is considered sufficient to assess the primary objective of this exploratory trial. With this sample size, the precisions of the ratio of the geometric means (test/reference) to be expected with 95% probability, are presented in [Table 7.7: 1](#). That is to say, we expect with 95% probability, that the precision is no greater than the value specified, where precision is defined as the ratio of upper CI limit to the point estimate of the geometric mean ratio.

Proprietary confidential information © 2016 Boehringer Ingelheim International GmbH or one or more of its affiliated companies

The observed ratio of the geometric means (and geometric coefficient of variation (gCV)) in previous trials (1297.8, [c03070713](#); 1297.6, CTR in reporting stage) were:

- 108% (45%) for $AUC_{(0-\infty)}$ in 1297.8
- 104% (54%) for $AUC_{(0-\infty)}$ in 1297.6
- 112% (32%) for C_{max} in 1297.6

The values from 1297.6 are estimated from the models adjusted for BMI (continuous). Although the main analysis for this study will be adjusted for baseline body weight (continuous), these model estimates serve as a good approximation, given the high correlation expected between BMI and body weight. The values coming from 1297.8 are unadjusted.

Table 7.7: 1 Precision and illustrative two-sided 90% confidence intervals around the ratios of geometric means (T/R) for different gCVs in a parallel trial (N=160).

gCV [%]	Precision upper CL / relative BA estimate	Ratio [%] *	Lower CL [%]	Upper CL [%]
32	1.09	112	102.44	122.45
45	1.13	108	95.53	122.09
54	1.16	104	90.01	120.17

*Ratio of geometric means (test/reference) for a PK endpoint is defined by $\exp(\mu_T)/\exp(\mu_R)$.

The calculation was performed as described by Julious ([R12-0972](#)) using R Version 3.2.2.

Regarding the assessment of the primary PK parameters, albeit in an exploratory manner, the following table ([Table 7.7: 2](#)) provides an overview of the probability of success (power) given some assumed effect sizes and assumptions on the gCV, as described above. The calculations are based upon the overall treatment effect, adjusting for BMI continuous (as a good substitute for body weight), where data is available.

Boehringer Ingelheim
BI Trial No.: 1297.13
c11534380-01

23 Aug 2016

Trial Protocol

Page 50 of 58

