7. STATISTICAL CONSIDERATIONS

7.1. ADJUSTMENTS FOR COVARIATES AND FACTORS TO BE INCLUDED IN ANALYSES

The following covariates and factors are used in the analyses. For details of their inclusion in the models, see the specific analysis section.

- Treatment group (BI 695501 using AI or BI 695501 using PFS)
- Baseline body weight (continuous variable)

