10. DEMOGRAPHIC AND OTHER BASELINE CHARACTERISTICS

Demographic data and other baseline characteristics will be presented for the RND, SAF and PKS.

In this trial, there is a high probability that RND is equivalent to SAF. In order to avoid duplicate tables regarding demographic characteristics, it will be checked before the final DBL whether:

- Subjects were treated but not randomized
- Subjects were randomized but not treated
- Subjects did not receive the allocated treatment

If RND is equivalent to SAF, tables will be displayed for RND only. Otherwise, both populations will be considered.

In the same manner, tables will be repeated for PKS only if PKS is not equivalent to RND.

No statistical testing will be carried out for demographic or other baseline characteristics.

The following demographic and other baseline characteristics will be reported for this trial:

- Age (years)

Document: \\weedc-nas01a\BIOSdata\Boehringer_Ingelheim\BI_695501\EYA00232\Biostatistics\Documentation\SAP\BI_1297_13_SAP_09JAN2017_v1.0

Author: [REDACTED] Version Number: 1.0
Version Date: 09JAN2017

Template No: CS_TP_BS016 Revision 4 Reference: CS_WI_BS005
Effective Date: 01Apr2016

Copyright © 2009, 2010, 2012, 2016 [REDACTED] Transnational Corp. All rights reserved.
The contents of this document are confidential and proprietary to [REDACTED] Transnational Corp. Unauthorized use, disclosure or reproduction is strictly prohibited.

[figure not shown]

Statistical Analysis Plan

- Age groups 1:
 - <65 years
 - ≥65 - <75 years
 - ≥75 years
- Age groups 2:
 - <65 years
 - ≥65 years
- Gender (Male / Female)
- Childbearing potential (Post-menopausal / Surgically sterile / Childbearing potential (includes tubal ligation))
- Race (American Indian or Alaska Native / Asian / Black or African American / Native Hawaiian or Other Pacific Islander / White / Other)
- Ethnicity (Hispanic or Latino / Not Hispanic or Latino / Not reported)
- Weight (kg)
- Weight groups (equivalent to the stratification factor):
 - ≤60.0 kg,
 - >60.0 - <90.0 kg,
 - ≥90.0 kg.
- Height (cm)
- Body mass index (BMI) (kg/m²)
- Smoking status (never smoked / is an ex smoker / currently smokes)
- Alcohol consumption (does not drink any alcohol / drinks alcohol but should not interfere with participation in trial / drinks alcohol and could interfere with participation in trial)

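### The exploratory exposure model adjusts for weight but not for sex; adding sex is a nearly free, modest gain in precision, not the correction of an error

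*Protocol*

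**What the plan says.** Protocol 7.1 describes an ANOVA on the log scale "with fixed effects for treatment, and baseline body weight (continuous"). It explains why site, a randomisation factor, is left out of the model. No visible text gives a reason for leaving sex out. SAP 7.1 lists the covariates and factors used in the analyses as treatment group and "Baseline body weight (continuous variable"), and nothing else.

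Sex is part of the design in other ways. The protocol synopsis states: "At least 30% of each gender will be included in the study". SAP 10 tabulates "Gender (Male / Female") at baseline. Protocol 7.6 stratifies randomisation by site and weight category only.

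Protocol 3.2 gives the rationale for weight: injection characteristics are "more likely influenced by the amount of s.c. fat tissue", with BMI and weight taken as correlates of that tissue.

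For planning, Protocol 7.7 uses gCVs of 45% (AUC0-∞, trial 1297.8) and of 54% (AUC0-∞) and 32% (Cmax) from trial 1297.6. Protocol 1.2 describes the subjects treated in 1297.1 and 1297.8 as male: "a total of 175 male healthy subjects were treated with 40 mg s.c. of BI 695501". On adjustment, Protocol 7.7 says "The values coming from 1297.8 are unadjusted", and "The values from 1297.6 are estimated from the models adjusted for BMI (continuous").

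**The concern.** On the protocol's own reasoning, weight is in the model because it stands in for subcutaneous fat. It is an imperfect proxy. If men and women of the same weight differ in exposure after a thigh injection, a weight-only model cannot remove that difference. Neither the randomisation strata nor the model controls the sex balance between devices directly.

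What is at stake is the width of the 90% CI for the device ratio, which addresses the primary objective. Protocol 7.7 has little slack: it expects more than 70% power on the expectation of lower variability than before, with no allowance for drop-outs. The trial is also open-label throughout, including data cleaning and preparation of the analysis (Protocol 4.1.5.1), so a covariate added after the data have been seen could look as if it had been chosen for its result.

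**Working it through.** **Inputs from the documents.** 160 subjects, 1:1, so 80 per arm; two-sided 90% CI; range 80–125%; gCV 45% and 54%; ratio 104% (Protocol 7.3.1, 7.6, 7.7).

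**Assumptions (not in the documents).** d = log difference in exposure between the sexes at equal weight, 0 to 0.30. Share of women p = 0.5. Correlation between sex and weight ρ = 0 unless stated. p = 0.5 and ρ = 0 give the sex term its largest effect.

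**1. Reproduce the plan's figures.** Log-scale variance is σ² = ln(1 + gCV²):
- gCV 45%: ln(1.2025) = 0.1844, σ = 0.429
- gCV 54%: ln(1.2916) = 0.2559, σ = 0.506

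Precision in Table 7.7:1 is exp{t(0.95; 158) × σ × √(χ²(0.95; 158)/158) × √(2/80)}, with t = 1.6546 and χ² = 188.33. This gives 1.130 and 1.155, against 1.13 and 1.16 in the table. Exact power of the two one-sided tests at a ratio of 104% is 84.0% (gCV 45%) and 68.8% (gCV 54%), against 83% and 68% in Table 7.7:2. The plan's figures reproduce closely enough to serve as a base.

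**2. Variance that a sex term would remove.** Removed variance = p(1−p) × d² × (1−ρ²). With p = 0.5 and ρ = 0 this is 0.25d².

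| d | Removed | Share of 0.1844 | Share of 0.2559 |
|---|---|---|---|
| 0.10 | 0.0025 | 1.4% | 1.0% |
| 0.20 | 0.0100 | 5.4% | 3.9% |
| 0.30 | 0.0225 | 12.2% | 8.8% |

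At gCV 45% the log-scale CI becomes narrower by 1 − √(1 − share): 0.7%, 2.7% and 6.3%.

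**3. Power at ratio 104% with sex in the model**, holding the total residual gCV at the planning value:

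| gCV | Weight only | d = 0.10 | d = 0.20 | d = 0.30 |
|---|---|---|---|---|
| 45% | 84.0% | 84.5% | 86.0% | 88.4% |
| 54% | 68.8% | 69.3% | 70.9% | 73.6% |

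**4. If sex and weight are correlated.** I simulated 6,000 trials per setting, with allocation balanced within the three weight categories and ρ = 0.5. At d = 0.20 and gCV 45%, power went from 84.1% to 85.1%, about one point.

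**5. If sex has no effect beyond weight (d = 0).** The weight-only model has 160 − 3 = 157 residual degrees of freedom; adding sex leaves 156. In the simulations the loss was 0.1 to 0.6 points of power, part of which is simulation noise.

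**6. Bias.** The mean difference between the device estimates with and without sex was zero to three decimals in all but one simulated setting, and 0.001 there (0.0006 before rounding, d = 0.30). Omission moves individual estimates by chance, not systematically.

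**7. Chance imbalance is not a second cost.** The SD of the between-arm difference in sex share is √(2 × 0.25/80) = 0.079. At d = 0.20 the resulting shift has SD 0.079 × 0.20 = 0.0158, and 0.0158² = 0.00025. The extra variance of the device estimate from the larger residual is (2/80) × 0.25 × 0.20² = 0.00025. The two are the same quantity: the wider CI is what covers the imbalance.

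**8. The all-male gCV.** Suppose the 45% excludes all sex variance and 0.25d² is added on top. Power at 104% falls from 84.0% to 83.5%, 81.9% and 79.3% for d = 0.10, 0.20 and 0.30. Even at d = 0.30 the variance is 0.1844 + 0.0225 = 0.2069, a gCV of about 48%, which is below the 50% and 54% rows already in Table 7.7:2.

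**The case against.** The case for leaving the model alone is substantial. No visible passage reports an exposure difference by sex at equal weight, so every size above zero is assumed. Weight is both a stratum and a covariate; to the extent that sex tracks weight, its effect is already partly balanced and absorbed, which helps the device comparison. The analysis is explicitly exploratory and primarily descriptive (Protocol 7.1 to 7.3, SAP 7.3), so a small change in CI width alters no pre-specified decision. A sex quota does not oblige anyone to fit a sex term. Parts of the PK analysis text are blacked out, so a sensitivity model or an exposure summary by sex may exist there.

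Most of this stands, and it sets the severity. It does not remove the point: Protocol 7.1 states the model in full, SAP 7.1 presents its list as the covariates used, and a recorded baseline variable can be added at almost no cost.

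Two stronger readings are tempting and are not supported. A reader might infer that the weight-only model distorts the ratio or invalidates its CI; under randomisation it does neither (steps 6 and 7). A reader might also infer that planning is optimistic because the 45% comes from men only. That figure lacks between-sex variance, but it is also unadjusted for weight, so it contains variance that the planned model should remove. The protocol also plans for 54%, from a trial whose sex mix is not stated.

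**Conclusion.** The point holds as a low-severity improvement. The weight-only model leaves in the residual any sex difference that weight does not explain, at some cost in precision. Under the most favourable assumptions for the term, the gain at a ratio of 104% is at most about 4 to 5 points of power at a log difference of 0.30, and about 2 points or less up to 0.20. It takes power across the 70% line only at gCV 54%, where the plan is already just below it (68.8%), and only for differences near the middle of the assumed range or above. If sex adds nothing beyond weight, nothing is gained and almost nothing is lost. These sizes rest on assumed sex effects. The model as written is valid, and the plan contains no error here.

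**What to change.** Before database lock, pre-specify sex (two levels) as a fixed effect alongside treatment and continuous baseline weight, in Protocol 7.1 and in SAP 7.1 and 16.1.3. Report the treatment-plus-weight model as the supportive analysis.

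The cost is one term in the model statement, using data already collected, and one residual degree of freedom of about 157. No change to sample size, randomisation or data collection is needed.
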